2 ANALYSIS SETS

2.1 Definition of Analysis Sets

Two main analysis sets are defined for this study for the analysis of patients who have been included in the study as part of the global enrolment.

Date 15 February 2022

Full analysis sets

Intention to treat (ITT): The primary statistical analysis of the efficacy of olaparib will include all patients who are randomised as part of the global enrolment. The primary analysis will compare the treatment groups on the basis of randomised treatment, regardless of the treatment actually received. Patients who were randomised as part of the global enrolment but did not subsequently go on to receive study treatment are included in the Full Analysis Set (FAS). Therefore, all efficacy and HRQoL data will be summarised and analysed using the FAS on an intention to treat (ITT) basis.

No centres will be provided with all of the treatment codes within that centre until completion of the study following the final analysis of overall survival.

Safety analysis set

All patients who received at least one dose of randomised investigational product, olaparib or placebo and are part of the global enrolment will be included in the safety analysis set (regardless of whether that was the randomised therapy intended or indeed whether, in rare cases, they received therapy without being randomised). Throughout the safety results sections, erroneously treated olaparib patients (those randomised to olaparib but actually received placebo) will be accounted for in the placebo treatment group. Erroneously treated placebo patients (those randomised to placebo but actually received olaparib) will be accounted for in the olaparib treatment group. Patients receiving treatment from more than one treatment arm will be accounted for based upon their initial treatment started

Table 1 Summary of Outcome Variables and Analysis Populations

Outcome Variable	Populations
Efficacy Data	
- PFS	FAS (ITT)
- OS, PFS2, TFST, TSST, TDT, symptom/HRQoL endpoints	FAS (ITT)
Study Population/ Demography Data	
- Demography characteristics (e.g. age, sex etc)	FAS (ITT)
- Baseline and disease characteristics	FAS (ITT)
- Important deviations	FAS (ITT)
- Medical/Surgical history	FAS (ITT)
- Previous anti-cancer therapy	FAS (ITT)
- Concomitant medications/procedures	FAS (ITT)
- Subsequent anti-cancer therapy	FAS (ITT)
Safety Data	
- Exposure	Safety
- Adverse Events	Safety
- Laboratory measurements	Safety
- ECGs	Safety
- Vital Signs	Safety

2.2 Violations and Deviations

The important protocol deviations will be listed and summarised by randomised treatment group. None of the deviations will lead to any patients being excluded from any of the analysis sets described in Section 2.1. If the deviations are serious enough to have the potential to impact the primary analysis, sensitivity analyses may be performed.

The following general categories will be considered important deviations and be listed and discussed in the CSR as appropriate.

- Patients randomised but who did not receive olaparib/matching placebo.
- Patients who deviate from key entry criteria, which will be documented ahead of database lock.
- Baseline RECIST scan > 28 days before study treatment is started

Date 15 February 2022

- Baseline RECIST scan after randomised treatment is started.
- Patients who have a RECIST scan outside of a scheduled visit window on > 2
 occasions.
- Disallowed concomitant medication use.

Misrandomisations in terms of errors in treatment dispensing patients receiving treatment other than that to which they were randomised as well as incorrect stratifications, will also be summarised and listed. A misrandomisation is when a patient is not randomised or treated according to the randomisation schedule. It is envisaged that there will be 2 sub categories of this:

- (a) Patients who receive no treatment whatsoever for a period of time due to errors in dispensing of medication. Note, this is not due to tolerability issues where patients may stop taking drug.
- (b) The patient receives a treatment pack with a different code to their randomisation code. However, the actual treatment may still match the randomised treatment. For example, a patient is given randomisation code 0001, which according to the randomisation schedule is olaparib. However, at the randomisation visit they are given treatment pack 0003, but this still contains olaparib.

Patients who receive the wrong treatment at any time will be included in the safety analysis set as described in Section 2.1. During the study, decisions on how to handle misrandomisations will be made on an individual basis with written instruction from the study team leader and the study statistician.

In addition to the programmatic determination of the deviations above, monitoring notes or summaries will be reviewed to determine any important post entry deviations that are not identifiable via programming, and to check that those identified via programming are correctly classified. The final classification will be made prior to database lock and all decisions will be made whilst blinded to study treatment allocation.

3 PRIMARY AND SECONDARY VARIABLES

3.1 Derivation of RECIST Visit Responses

Patients with measurable or non measurable disease or no evidence of disease assessed at baseline by CT/MRI will be entered in this study. RECIST 1.1 has been modified to allow the assessment of progression due to new lesions in patients with no evidence of disease at baseline.

For all patients, the RECIST tumour response data will be used to determine each patient's visit response according to modified RECIST version 1.1. It will also be used to determine if and when a patient has progressed in accordance with RECIST and also their best objective response (BoR).

Baseline radiological tumour assessments are to be performed no more than 28 days before randomisation and ideally should be performed as close as possible to the start of study treatment. Tumour assessments are then performed every 12 weeks (± 1 week) up to 156 weeks and then every 24 weeks (± 1 week) following randomisation until disease progression.

If an unscheduled assessment was performed and the patient had not progressed, every attempt should be made to perform the subsequent assessments at their scheduled visits. This schedule is to be followed in order to minimise any unintentional bias caused by some patients being assessed at a different frequency than other patients.

At each visit, an overall visit response will be determined - using the information from target lesions (TL), non-target lesions (NTL) and new lesions. For the investigator assessments this will be done programmatically and the RECIST outcomes will be calculated using a computer program.

3.1.1 Target lesions (TLs)

Measurable disease is defined as having at least one measurable lesion, not previously irradiated, which is ≥ 10 mm in the longest diameter (LD) (except lymph nodes which must have short axis ≥ 15 mm) with CT or MRI and which is suitable for accurate repeated measurements.

A patient can have a maximum of 5 measurable lesions recorded at baseline with a maximum of 2 lesions per organ (representative of all lesions involved suitable for accurate repeated measurement) and these are referred to as target lesions (TLs). If more than one baseline scan is recorded then measurements from the one that is closest to randomisation will be used to define the baseline sum of TLs. It may be the case that, on occasion, the largest target lesion does not lend itself to reproducible measurement in which circumstance the next largest lesion, which can be measured reproducibly, should be selected.

All other lesions (or sites of disease) not recorded as TL should be identified as NTL at baseline. Measurements are not required for these lesions, but their status should be followed at subsequent visits.

Note: For patients who do not have measurable disease at entry (i.e. no TLs) but have non-measurable disease, evaluation of overall visit responses will be based on the overall NTL assessment and the absence/presence of new lesions (see Section 3.1.3 for further details). If a patient does not have measurable disease at baseline then the TL visit response will be not applicable (NA).

For patients with no evidence of disease (NED) at baseline (i.e. no TLs and no NTLs), evaluation of overall visit responses will be based on absence/presence of new lesions. If no TLs and no NTLs are recorded at a visit, both the TL and NTL visit response will be recorded as NA and the overall visit response will be NED.

Table 2 TL Visit Responses

Visit Responses	Description
Complete Response (CR)	Disappearance of all target lesions since baseline. Any pathological lymph nodes selected as target lesions must have a reduction in short axis to <10 mm
Partial Response (PR)	At least a 30% decrease in the sum of diameters of TL, taking as reference the baseline sum of diameters
Progressive Disease (PD)	At least a 20% increase in the sum of diameters of target lesions taking as reference the smallest sum on study (this includes the baseline sum if that is the smallest on study). In addition to the relative increase of 20%, the sum must also indicate an absolute increase of at least 5 mm
Stable Disease (SD)	Neither sufficient shrinkage to qualify for PR nor sufficient increase to qualify for PD
Not Evaluable (NE)	Only relevant if any of the target lesions were not assessed or not evaluable or had a lesion intervention at this visit. Note: If the sum of diameters meets the progressive disease criteria, progressive disease overrides not evaluable as a target lesion response
Not Applicable (NA)	No target lesions are recorded at baseline

The percentage increase/decrease taking baseline as a reference for post-baseline visit will be calculated as:

[Post-baseline sum of diameters of TL - Baseline sum of diameters of TL] *100/ (Baseline sum of diameters of TL)

And similarly for the percentage change at a post-baseline visit using previous study minimum as a reference. If more than one baseline scan is recorded then measurements from the one that is closest to and prior to randomisation will be used to define the baseline sum of diameters of TLs.

Rounding of TL data

For calculation of PD and PR for TLs, percentage changes from baseline and previous minimum should be rounded to 1 decimal place. before assigning a TL response. For example 19.95% should be rounded to 20.0% but 19.94% should be rounded to 19.9%

Missing TL data

For a visit to be evaluable, all target lesion measurements should be recorded. However, a visit response of PD should still be assigned if any of the following occurred:

- A new lesion is recorded.
- A NTL visit response of PD is recorded.
- The sum of TLs is sufficiently increased to result in a 20% increase, and an absolute increase of ≥ 5mm, from nadir even assuming the non-recorded TLs have disappeared. Note: the nadir can only be taken from assessments where all the TLs had a LD recorded.

Lymph nodes

For lymph nodes, if the size reduces to < 10 mm then these are considered non-pathological. However a size will still be given and this size should still be used to determine the TL visit response as normal. In the special case where all lymph nodes are < 10 mm and all other TLs are 0 mm then although the sum may be > 0 mm the calculation of TL response should be over-written as a CR.

TL visit responses subsequent to CR

A CR can only be followed by CR, PD or NE. If a CR has occurred then the following rules at the subsequent visits must be applied:

- Step 1: If all TLs meet the CR criteria (i.e. 0 mm or < 10 mm for lymph nodes) then response will be set to CR irrespective of whether the criteria for PD of TL is also met i.e. if a lymph node LD increases by 20% but remains < 10 mm.
- Step 2: If some TL measurements are missing but all other lesions meet the CR criteria (i.e. 0 mm or < 10 mm for lymph nodes) then response will be set to NE irrespective of whether when referencing the sum of TL diameters the criteria for PD is also met.
- Step 3: If not all TLs meet the CR criteria and the sum of lesions meets the criteria for PD then response will be set to PD
- Step 4: If after steps 1-3 a response can still not be determined the response will be set to remain as CR

TL too big to measure

If a TL becomes too big to measure this should be indicated in the database and a size ('x') above which it cannot be accurately measured should be recorded. If using a value of x in the calculation of TL response would not give an overall visit response of PD, then this will be flagged and reviewed by the study team blinded to treatment assignment. It is expected that a visit response of PD will remain in the vast majority of cases.

TL too small to measure

If a TL becomes too small to measure a value of 5 mm will be entered into the database and used in TL calculations, unless the radiologist has indicated and entered a smaller value that can be reliably measured. If a TL response of PD results then this will be reviewed by the study team blinded to treatment assignment.

Irradiated lesions/lesion intervention

Previously irradiated lesions (i.e. lesion irradiated prior to entry into the study) should be recorded as NTLs and should not form part of the TL assessment.

Any TL (including lymph nodes), which has had intervention during the study (for example, irradiation / palliative surgery / embolisation), should be handled in the following way and once a lesion has had intervention then it should be treated as having intervention for the remainder of the study noting that an intervention will most likely shrink the size of tumours:

- Step 1: the diameters of the TLs (including the lesions that have had intervention) will be summed and the calculation will be performed in the usual manner. If the visit response is PD this will remain as a valid response category.
- Step 2: If there was no evidence of progression after step 1, treat the lesion diameter (for those lesions with intervention) as missing and scale up as described below as long as there remain ≤ 1/3 of the TLs with missing measurements. If the scaling results in a visit response of PD then the patient would be assigned a TL response of PD.
- Step 3: If after both steps PD has not been assigned, then if appropriate, a scaled sum of diameters will be calculated (as long as $\leq 1/3$ of the TLs have interventions, and PR or SD then assigned as the visit response. Patients with intervention are evaluable for CR as long as all non-intervened lesions are 0 (or <10mm for lymph nodes) and each lesion that has experienced intervention also has a value of 0 recorded. If scaling-up is not appropriate due to too few non-missing measurements then the visit response will be set as NE.

If $\leq 1/3$ of the TL measurements have interventions then the results will be scaled up based on the measurements at the nadir visit to give an estimated sum of diameters and this will be used

in calculations; this is equivalent to comparing the visit sum of diameters of the nonintervention lesions to the nadir sum of diameters excluding the lesions with interventions.

Example of scaling

Lesion	Longest diameter at nadir visit	Longest diameter at follow-up visit
1	7.2	7.1
1	1.2	7.1
2	6.7	6.4
3	4.3	4.0
4	8.6	8.5
5	2.5	Intervention
Sum	29.3	26

Lesion 5 has had an intervention at the follow-up visit.

The sum of lesions 1-4 at the follow-up is 26 cm. The sum of the corresponding lesions at baseline visit is 26.8 cm.

Scale up as follows to give an estimated TL sum of 28.4cm:

$$\frac{26}{26.8} \times 29.3 = 28.4$$
cm

$$\frac{26}{26.8} \times 29.3 = 28.4$$
cm

At subsequent visits the above steps will be repeated to determine the TL and overall visit response. When calculating the previous minimum, lesions with intervention should be treated as missing and scaled up where appropriate (as per step 2 above).

Lesions that split in two

If a TL splits in two, then the LDs of the split lesions should be summed and reported as the LD for the lesion that split.

Lesions that merge

If two TLs merge, then the LD of the merged lesion should be recorded for one of the TL sizes and the other TL size should be recorded as 0 mm.

Change in method of assessment of TLs

CT and MRI are the only methods of assessment that can be used within the trial. If a change in method of assessment occurs between CT and MRI, this will be considered acceptable and no adjustment within the programming is needed.

If a change in method involves clinical examination (e.g. CT changes to clinical examination or vice versa), any affected lesions should be treated as missing.

3.1.2 Non-target lesions (NTLs) and new lesions.

At each visit an overall assessment of the NTL response should be recorded by the investigator. This section provides the definitions of the criteria used to determine and record overall response for NTL at the investigational site at each visit.

NTL response will be derived based on the investigator's overall assessment of NTLs as follows:

Table 3 NTL Visit Responses

	1
Visit Responses	Description
Complete Response (CR)	Disappearance of all NTLs present at baseline with all lymph nodes non-pathological in size (<10 mm short axis).
Progression (PD)	Unequivocal progression of existing non-target lesions. Unequivocal progression may be due to an important progression in one lesion only or in several lesions. In all cases the progression MUST be clinically significant for the physician to consider changing (or stopping) therapy.
Non-CR/Non-PD	Persistence of one or more NTLs with no evidence of progression.
Not Evaluable (NE)	Only relevant when one or some of the non-target lesions were not assessed and, in the investigator's opinion, they are not able to provide an evaluable overall non-target lesion assessment at this visit.
	Note: For patients without target lesions at baseline, this is relevant if any of the non-target lesions were not assessed at this visit and the progression criteria have not been met.
Not Applicable (NA)	Only relevant if there are no NTLs at baseline
Not Applicable (NA)	Only relevant if there are no IVILs at baseline

To achieve 'unequivocal progression' on the basis of NTLs, there must be an overall level of substantial worsening in non-target disease such that, even in presence of SD or PR in TLs, the overall tumour burden has increased sufficiently to merit discontinuation of therapy. A modest 'increase' in the size of one or more NTLs is usually not sufficient to qualify for unequivocal progression status.

Details of any new lesions will also be recorded with the date of assessment. The presence of one or more new lesions is assessed as progression.

A lesion identified at a follow up assessment in an anatomical location that was not scanned at baseline is considered a new lesion and will indicate disease progression.

The finding of a new lesion should be unequivocal: i.e. not attributable to differences in scanning technique, change in imaging modality or findings thought to represent something other than tumour.

New lesions will be identified via a Yes/No tick box. The absence and presence of new lesions at each visit should be listed alongside the TL and NTL visit responses.

A new lesion indicates progression so the overall visit response will be PD irrespective of the TL and NTL response.

If the question 'Any new lesions since baseline' has not been answered with Yes or No and the new lesion details are blank this is not evidence that no new lesions are present and should be treated as NE in the derivation of overall visit response.

Symptomatic deterioration is not a descriptor for progression of NTLs: it is a reason for stopping study therapy and will not be included in any assessment of NTLs.

Patients with 'symptomatic deterioration' requiring discontinuation of treatment without objective evidence of disease progression at that time should continue to undergo tumour assessments where possible until objective disease progression is observed.

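### SAP 3.1.1: after a target-lesion complete response, Step 4 scores a visit with an unmeasured lesion as CR if another lesion has regrown short of PD, but Step 2 scores it NE if nothing has regrown

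*SAP*

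**What the plan says.** SAP section 3.1.1 limits what may follow a target-lesion (TL) complete response: "A CR can only be followed by CR, PD or NE". Four steps are then applied in order.

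- The first keeps CR when every TL is still at 0 mm, or under 10 mm if it is a node.
- The second, which leads to NE, has this condition: "If some TL measurements are missing but all other lesions meet the CR criteria".
- The third assigns PD when at least one TL no longer qualifies for CR and the summed diameters satisfy the PD definition.
- The fourth takes whatever is left: "Step 4: If after steps 1-3 a response can still not be determined the response will be set to remain as CR".

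The same section has a general rule for missing TL data: "For a visit to be evaluable, all target lesion measurements should be recorded". Every exception listed there leads to PD: a new lesion, non-target PD, or a measured sum at least 20% and at least 5 mm above nadir with the unrecorded TLs counted as gone. The nadir may be taken only from visits at which all TLs were measured. The NE row of Table 2 covers any TL that was not assessed or not evaluable, and only PD overrides it.

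The percentage formula is written with baseline as the denominator, followed by: "And similarly for the percentage change at a post-baseline visit using previous study minimum as a reference". Nothing is said about a minimum of 0 mm. Table 2 asks for an absolute rise of at least 5 mm, whereas section 3.2.1 asks for more than 5 mm.

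**The concern.** Step 4 has a sensible purpose. When every TL has been measured and there is some regrowth below the PD threshold, the only permitted answers are CR, PD and NE, so CR is carried forward. But nothing confines Step 4 to fully measured visits. A visit with an unmeasured TL and sub-threshold regrowth fails Step 1 (not all TLs meet CR), Step 2 (the measured ones do not all meet CR) and Step 3 (PD not met), and so becomes CR. The same visit without the regrowth is NE.

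Investigator PFS is the primary endpoint, and section 3.1 says its RECIST outcomes are calculated by program, so the literal rule matters. What is at stake is whether the visit counts as evaluable. Under section 3.2.1 the last evaluable assessment fixes the censoring date and starts the interval for the two-missed-visit rule.

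**Working it through.** No stated sample size, power or alpha depends on this rule, so there is no plan figure to reproduce. The check applies Steps 1 to 4 literally.

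**Inputs.** A TL meets CR at 0 mm, or below 10 mm for a node. PD requires (sum − minimum) × 100 / minimum ≥ 20.0 and, by Table 2, sum − minimum ≥ 5 mm. An unmeasured TL contributes 0 to the sum.

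**1. Unmeasured lesion after CR**

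| State at CR (minimum sum) | Next visit | Rise over minimum | Result |
|---|---|---|---|
| Nodes 8 + 8 (16 mm) | one unmeasured, other 8 | 8 − 16 = −8 mm | NE (Step 2) |
| same | one unmeasured, other 10 | 10 − 16 = −6 mm | CR (Step 4) |
| same | one unmeasured, other 20 | 20 − 16 = +4 mm (+25.0%) | CR (Step 4) |
| same | one unmeasured, other 22 | 22 − 16 = +6 mm (+37.5%) | PD (Step 3) |
| Nodes 8 + 7, liver 0 (15 mm) | liver unmeasured, nodes 8 + 7 | 0 mm | NE (Step 2) |
| same | liver unmeasured, nodes 11 + 7 | 18 − 15 = +3 mm (+20.0%) | CR (Step 4) |
| Node 9, other lesion 0 (9 mm) | node unmeasured, lesion 13 | 13 − 9 = +4 mm (+44.4%) | CR (Step 4) |
| same | node unmeasured, lesion 15 | 15 − 9 = +6 mm (+66.7%) | PD (Step 3) |

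As the measured disease grows, the score runs NE, CR, PD. The missing-data rule and Table 2 would give NE, NE, PD.

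**2. Effect on evaluability.** In Table 4, with no new lesion and no non-target PD, TL NE gives overall NE. TL CR gives overall CR (non-target CR or not applicable) or PR (non-target non-CR/non-PD or NE).

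**3. Effect on PFS.** Take a constructed patient with a full scan at week 24 and a partial visit with sub-threshold regrowth at week 36.

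- If there is no later scan, PFS is censored at week 24 when week 36 is NE, and at week 36 when it is CR. The shift is 36 − 24 = 12 weeks. On the schedule after week 156 it would be 24 weeks.
- Suppose instead that week 48 is missed and PD is found at week 60. For a last evaluable scan this early, section 3.2.1 sets two missed visits at more than 26 weeks. With week 36 NE, the gap is 60 − 24 = 36 weeks, so the patient is censored at week 24. With week 36 CR, the gap is 60 − 36 = 24 weeks, so PD at week 60 counts as an event.

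**4. Effect on the PD call.** PD is not met at the affected visit under either scoring. The partial visit cannot set the nadir, so the reference for later visits is unchanged.

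**5. Minimum of 0 mm, all TLs measured.** Table 2 can be read as sum ≥ 1.2 × minimum with a rise of at least 5 mm. Regrowth of 2 or 4 mm is then CR, and 5, 6, 12 or 30 mm is PD at Step 3. The printed formula divides by 0. Only if a program treats that undefined value as not PD do these last four become CR. At exactly 5 mm the answer also depends on which of the two absolute criteria applies. That value can arise in practice, because section 3.1.1 enters 5 mm for a TL too small to measure.

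**The case against.** **The general rule could be said to settle it.** One could argue that the missing-data rule already makes the visit non-evaluable, so a response is determined and Step 4 is never reached. The SAP gives no such precedence. Step 4 refers only to Steps 1 to 3. Step 2 deals with missing TLs inside the sequence, which would be unnecessary if the general rule governed.

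**Three stronger readings are tempting, and the documents do not support them.**

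- *Any unmeasured lesion with regrowth is scored CR.* Step 3 and the missing-data rule give PD once the measured sum reaches the threshold, and a new lesion or non-target PD overrides in any case.
- *Relapse from a zero sum is scored CR instead of PD.* A rise from 0 to 18 mm is PD on an ordinary reading of Table 2 and Step 3. If a zero minimum could never give PD, Step 3 would be unreachable for every patient whose TLs are all non-nodal, although the section says PD may follow CR. What is missing is a stated convention.
- *Progressions are lost or delayed.* In the missing-lesion case PD is not met, the correct score is NE, and the nadir is unaffected.

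**The timing limits the consequence.** The SAP is dated 15 February 2022, and its section 5 describes the PFS analysis as done. No further PFS analysis is planned unless health authorities request one, and the planned OS analyses do not use these steps. This stands.

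**There are partial checks.** The central-review analysis uses the reviewers' own time-point responses, and disagreements with the investigator are tabulated by arm. The attrition-bias analysis restores events that follow two or more non-evaluable assessments. Neither corrects the primary derivation. Protocol Appendix F, which holds the modified RECIST guidance, is not in the available text and might address recurrence after CR.

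**Conclusion.** The point holds in its narrow form. For a visit with an unmeasured TL after TL CR, Step 4 gives sub-threshold regrowth a better and evaluable score than no regrowth. That contradicts the missing-data rule in the same section and the NE row of Table 2, and nothing else in the SAP repairs it.

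The effect is on evaluability: a censoring date nominally one scan interval later per affected visit, and a restarted two-missed-visit count that can decide whether a later progression is counted. Exposure needs TLs at baseline, a TL CR, a later visit with a TL unmeasured, and regrowth short of PD. The documents give no count of such patients, so neither the size nor the direction of any effect on the hazard ratio can be computed. It is likely to touch few patients, and it matters only if investigator PFS is re-derived. The conclusion assumes that the steps are programmed as written.

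The zero-minimum gap is secondary. It is a convention to state, and it is not evidence that relapses were scored as CR.

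**What to change.** Replace Step 4 with: *If any TL is missing or not evaluable and PD is not met, the response is NE; otherwise it remains CR.* Step 3 still comes first, so PD keeps precedence.

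As a clarification, add to Step 3: *If the previous minimum sum is 0 mm, the 20% criterion is taken as met and the absolute 5 mm criterion decides.* Then reconcile the absolute criterion between Table 2 and the missing-data rule (at least 5 mm) and sections 3.2.1 and 6 (more than 5 mm).

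The cost is two sentences, one wording correction and a small programming change. Because the primary analysis has been done, the sponsor should first establish how the existing program scored these visits and list any affected, by arm. If there are none, a note to that effect is enough. If there are some, the amended rule should be documented as a post-analysis correction and applied in any further derivation of investigator PFS.
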